4.6.2.2. Sensitivity Analyses

 A Cochran-Mantel-Haenszel (CMH) test will be used to test the null hypothesis of no treatment effect at Month 3 for each linzagolix group vs. placebo with regards to the proportion of subjects with a response for DYS and NMPP. Odds ratios will be estimated from the CMH test together with the associated 97.5% confidence intervals (CIs) and corresponding Bonferroni corrected pvalues. The proportion per treatment arm will be displayed together with exact Clopper-Pearson 95% CIs.

PROC FREQ (SAS Institute) will be used for the statistical analysis.

Sample SAS code (may be updated at analysis stage to fit the data):

Sponsor:	ObsEva		
Protocol:	18-OBE2109-003		
Document Version No.:	V5.0 Document Date: 13-JUN-2022		

Cochran-Mantel-Haenszel (CMH) test (to be performed pairwise).

```
PROC FREQ data=dataset;
	Tables Treatment*Response /CMH RELRISK RISKDIFF alpha=0.025;
	Where treatment in ();
	ods output riskdiffcol2=diff2 cmh=cmh commonrelrisks=cmrr;Run;
	data pvals_mult2 ;
		set cmh ;
		where ALTHYPOTHESIS="General Association" ;
		pval_vs_trt1=prob * 2 ;
			if pval_vs_trt1 > 1 then pval_vs_trt1 = 1;
	run;
```

Note: Response is coded as 1 for responders and 0 for non-responders.

 A sensitivity analysis will be performed, including in the definition of a responder any analgesic medication also taken for non-endometriosis associated pain. Information will be based on the concomitant medications collected in the eCRF during the two baseline menstrual cycles and the same calendar days as used for the assessment of pelvic pain (DYS and NMPP) for the 28 days prior to Month 3 visit.

Concomitant medications in the study identified as analgesics and opioids will be reviewed and confirmed by the Sponsor and be provided in an excel file prior to Database Lock. These may include any medication with one of the following ATC codes from the WHO drug dictionary version March 2016:

Table 6 List of ATC codes for analgesics and opioids

ATC code	Description	
A03D	Antispasmodics in combination with analgesics	
ΑΟ3ΕΑ	Antispasmodics, psycholeptics and analgesics in combination	

CRS-BS-TP-000005 V 1.0

Cytel Confidential: This is a controlled document and shall not be changed, saved, copied or reproduced by any unauthorized person.

Sponsor:	ObsEva		
Protocol:	18-OBE2109-003		
Document Version No.:	V5.0	Document Date:	13-JUN-2022

СОЗАН	Thiazides, combinations with psycholeptics and/or analgesics	
M01	Anti-inflammatory and anti-rheumatic products	
M02	Topical products for joint and muscular pain	
M03	Muscle relaxants	
N02	Analgesics	
N07BC	Drugs used in opioid dependence	
S02DA	Analgesics and anesthetics	

Among those analgesic medications, all medications with Pharmacological Subgroup (3rd level of the ATC classification) equal to 'OPIOIDS' (ATC code = N02A) will be considered as opiate medications. Other analgesic medications will be considered as non-opiate medications.

The increase/stable/decrease status of analgesic use will be defined in a blinded fashion case by case after review of the blinded data, and prior to Database Lock.

Analyses described in Section 4.6.2.1.2 will be repeated using the new responder definition.

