4.2.6. Subpopulations

Subgroup analyses will be performed for each co-primary endpoint and for BMD.

Subgroups include:

- Race: Black or African American, Other
- Ethnicity: Hispanic or Latino, Not Hispanic or Latino
- Age group 1 (<median value at baseline, ≥ median value at baseline) (based on FAS population)
- Age group 2 (<25, ≥ 25 to < 35, ≥ 35 to < 45, ≥ 45)
- Weight: < median value at baseline, ≥ median value at baseline (based on FAS population)
- BMI group 1 (< median value at baseline, ≥ median value at baseline) (based on FAS population)
- BMI group 2 (< 20, ≥ 20 to < 25, ≥ 25 to < 30, and ≥ 30)

CRS-BS-TP-000005 V 1.0

Page 38 of 127

Cytel Confidential: This is a controlled document and shall not be changed, saved, copied or reproduced by any unauthorized

Sponsor:	ObsEva		
Protocol:	18-OBE2109-003		
Document Version No.:	V5.0 Document Date: 13-JUN-2022		13-JUN-2022

- Baseline analgesic use: Subjects who took no rescue medication for endometriosis pain at baseline, subjects who took any NSAIDS and Narcotics at baseline
- Baseline pain VRS scores for dysmenorrhea (DYS), non-menstrual pelvic pain (NMPP), and dyspareunia: < median value at baseline, ≥ median value at baseline (based on FAS population)
- Time since endometriosis diagnosis (time in years): < 2 years, $\ge 2 < 5$ years, and ≥ 5 years
- History of pregnancy at baseline Yes, No

A subgroup analysis will be performed for the secondary endpoint of dyspareunia on subjects who have a mean dyspareunia score >1 at baseline. Detailed analysis is described in Section 4.6.

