4.6.2.1.2. Primary Efficacy Analysis

The primary efficacy analysis will be conducted using the FAS.

The analysis of each co-primary endpoint will be conducted using a logistic regression model, with treatment group as the main effect (three values) and including the baseline pain score as a covariate. Individual linzagolix versus placebo treatment group comparisons will be made using the same logistic regression model. Estimated odds-ratios and 97.5% intervals of proportions of responders of linzagolix treatment groups versus placebo will be presented, along with Bonferroni corrected p-values. Estimates of proportions of responders with 95% confidence intervals will be presented as well, estimated at the overall mean baseline pain score.

SAS Code (may be updated at analysis stage to fit the data):

```
PROC LOGISTIC data=dataset order=internal;
Class treatment(ref=placebo) / param=glm ;
Model resp(event= "Yes")= treatment base_pain /alpha=0.05;
Oddsratio treatment ;
Lsmeans treatment / ilink exp cl alpha=0.05 at means diffs=control('1')
adjust=bon;
Ods output OddsRatiosWald=or ModelANOVA=ma ParameterEstimates=pe
lsmeans=lsm diffs=diffs;
```

Run;

In addition, the mean pelvic pain scores for DYS and NMPP and change from baseline for the last 28 days prior to Month 3 or the last 28 days of treatment (or less) for subjects who discontinued will be summarized as continuous variables by treatment group. Cumulative distribution functions (CDF) for change from baseline at Month 3 for DYS and NMPP will be provided, with separate lines for each treatment group. The x-axis will present the different values for the DYS or NMPP change from baseline, and the y-axis will present the proportion of subjects reaching each value of change. Vertical lines of the relevant MCT thresholds obtained at the Month 3 responder threshold analysis will be displayed on the plots.

The number and percentage of subjects with:

- Reduction of X for DYS,
- Reduction of X for NMPP,

Sponsor:	ObsEva		
Protocol:	18-OBE2109-003		
Document Version No.:	V5.0 Document Date: 13-JUN-2022		

- Stable or decreased use of analgesics for EAP during bleeding days, during non-bleeding days, and overall,
- Reduction of X for DYS and stable or decreased use of analgesics for EAP (during bleeding days),
- Reduction of X for NMPP and stable or decreased use of analgesics for EAP (during non-bleeding days),

will be presented.

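### In the CMH sensitivity analysis of the co-primary endpoints, a single alpha in the SAS code gives 97.5% exact intervals for the per-arm proportions where the text promises 95%

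*SAP*

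**What the plan says.** SAP 4.6.2.2 tests each linzagolix group against placebo on the Month 3 response proportions for dysmenorrhea (DYS) and non-menstrual pelvic pain (NMPP). It sets two confidence levels. Odds ratios from the CMH analysis get 97.5% intervals with Bonferroni-corrected p-values. For the arms themselves, "The proportion per treatment arm will be displayed together with exact Clopper-Pearson 95% CIs".

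The code below that text has one TABLES statement, "Tables Treatment*Response /CMH RELRISK RISKDIFF alpha=0.025", and saves its results with "ods output riskdiffcol2=diff2 cmh=cmh commonrelrisks=cmrr;Run". A note adds: "Response is coded as 1 for responders and 0 for non-responders". There is no second call at another alpha.

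Neither text nor code names a stratifying variable. The primary logistic regression in SAP 4.6.2.1.2 is fitted "with treatment group as the main effect (three values) and including the baseline pain score as a covariate", and that section also reports per-arm proportions with 95% intervals. Randomization is unstratified (SAP 2.2).

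**The concern.** The text sets two confidence levels and the code sets one. A programmer who follows the code fills a table column headed 95% with 97.5% limits. Per-arm intervals in the primary and sensitivity tables would then carry the same label at different levels, and a reader setting them side by side would see extra width that has nothing to do with the data.

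The second, smaller matter is what the CMH odds ratio estimates. With one stratum it is the crude 2x2 odds ratio, whereas the primary model gives an odds ratio conditional on baseline pain. Odds ratios are not collapsible, so the two can differ in size even when the primary model is exactly right. The SAP does not tell the reader this.

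**Working it through.** **Inputs.** From SAP 4.1: 150 subjects per arm; DYS response 14.6% (placebo), 48.6% (75 mg), 64.7% (200 mg); NMPP response 18.8% (placebo), 42.1% (active). From SAP 4.2.5: p-values are doubled, so each comparison is two-sided at 0.025.

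**1. The plan's own figure.** Power = Φ{[(p1−p0)√n − z√(2p̄q̄)] / √(p0q0+p1q1)}, with z = 2.241 and p̄ the mean of the two rates (q = 1−p throughout). For NMPP, p̄ = 0.3045, and the formula gives Φ{[0.233×12.247 − 2.241×0.651]/0.630} = Φ(2.22) = 98.7%. Both DYS comparisons exceed 99.9%. Joint power is about 98.7% for each dose, so the stated power above 95% reproduces and the rates are read as the plan reads them.

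**2. Level produced by the code.** In standard PROC FREQ behaviour, the alpha on the TABLES statement sets every interval that the statement produces. RiskDiffCol2 holds the row proportions for the second response column, with their exact limits. With 0/1 coding, that column is the responders. So alpha=0.025 gives 97.5% limits (z = 2.241) for the odds ratio, as intended, and also for the per-arm proportions, where the text wants 95% (z = 1.960).

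**3. Size.** Clopper-Pearson limits for x out of n are the α/2 quantile of Beta(x, n−x+1) and the 1−α/2 quantile of Beta(x+1, n−x). At the planning rates, rounded to whole subjects:

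| Arm | x/150 | 95% (text) | 97.5% (code) | Width ratio |
|---|---|---|---|---|
| DYS placebo | 22 | 9.4-21.4% | 8.8-22.3% | 1.134 |
| DYS 75 mg | 73 | 40.4-56.9% | 39.3-58.1% | 1.136 |
| DYS 200 mg | 97 | 56.4-72.3% | 55.3-73.3% | 1.135 |
| NMPP placebo | 28 | 12.8-25.8% | 12.1-26.9% | 1.135 |
| NMPP active | 63 | 34.0-50.3% | 32.9-51.5% | 1.136 |

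**4. CMH with one stratum.** The statistic is Pearson's chi-square × (N−1)/N. For NMPP (28/150 v 63/150) this is 19.32 × 299/300 = 19.26. The odds ratio is (122×63)/(28×87) = 3.16, 97.5% CI 1.73-5.74, identical to a logistic regression without the covariate. The same calculation gives 5.52 for DYS 75 mg and 10.65 for DYS 200 mg.

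**5. Crude against conditional odds ratio.** The documents give no association between baseline pain and response, so it is assumed: logistic response, normal baseline score, intercepts solved to return the planned NMPP rates. The crude odds ratio from the unrounded rates is (0.421/0.579)/(0.188/0.812) = 3.14.

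| Assumed baseline odds ratio per SD | 1 | 1.25 | 1.5 | 2 | 3 |
|---|---|---|---|---|---|
| Conditional odds ratio, NMPP | 3.14 | 3.18 | 3.26 | 3.49 | 4.02 |
| Excess over crude | 0% | 1.2% | 3.8% | 11% | 28% |

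Over the same range the excess is 0 to 44% for DYS 75 mg and 0 to 69% for DYS 200 mg.

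**6. What stratifying would do.** For assumed shifts of 0.5, 1.0 and 1.5 log odds per SD (NMPP), the conditional odds ratio is 3.32, 3.87 and 4.79. A median split gives a Mantel-Haenszel odds ratio of 3.25, 3.56 and 4.00. At 1.0 it closes (3.56−3.14)/(3.87−3.14) = 58% of the gap. Quartiles give 3.30, 3.76 and 4.51, closing (3.76−3.14)/(3.87−3.14) = 85% at 1.0.

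**The case against.** On the interval level, the block is introduced with "Sample SAS code (may be updated at analysis stage to fit the data", and the text states the intended 95% plainly. The affected limits are descriptive, err on the wide side and sit in one sensitivity table. All of that stands and keeps the matter small. It does not remove the mismatch: the code is the only implementation given, and nothing in it signals that a second level is needed.

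On the missing stratum, a reader might infer that the CMH is misspecified, that its odds ratio cannot be compared with the primary one, or that agreement or disagreement between them says nothing about robustness. The documents do not support this. The text names no stratum, the code matches the text, and randomization is unstratified. Both analyses address the same null of no treatment effect, with the same 97.5% level and the same doubling of p-values. An unadjusted check of an adjusted result is legitimate, and the primary model is already repeated within baseline-pain subgroups (SAP 4.6.2.4).

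A reader might also infer that the CMH must show a smaller odds ratio and a materially weaker test. That depends on an association the documents do not give. At the planned NMPP rates, the crude comparison already has 98.7% power. There is some reason to expect an association: response needs an absolute fall of 1.10 (DYS) or 0.80 (NMPP) under SAP 4.6.1.3, so a subject whose baseline mean is below the threshold cannot respond. For NMPP, the VRS entry criterion requires only two moderate or severe non-bleeding days per cycle (protocol 9.2.1), so such a mean is possible. The strength of the association remains unknown.

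**Conclusion.** The text and code of SAP 4.6.2.2 disagree on the level of the per-arm exact intervals. Run as written, they are 97.5% intervals under a 95% label, 13 to 14% too wide at the planned rates. This rests on standard PROC FREQ handling of alpha and on the code being run unchanged.

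The absence of a stratum is not an error. It means only that the CMH odds ratio is marginal and should be described as such. Agreement with the primary analysis can be judged on direction and significance; a difference in size should not be read as lack of robustness.

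The point is minor. It touches one sensitivity table and no trial conclusion.

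**What to change.** Split the request in two:

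- For the test and odds ratio, keep `Tables Treatment*Response / CMH alpha=0.025`, saving CMH and CommonRelRisks.
- For the per-arm proportions, run a second PROC FREQ with `Tables Treatment*Response / RISKDIFF alpha=0.05`, saving RiskDiffCol2. If a risk difference from placebo is also to be shown, state its level separately.

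Then either add a sentence saying that the CMH odds ratio is unadjusted and is to be compared with the primary one in direction and significance, or use `Tables BasePainCat*Treatment*Response / CMH alpha=0.025`. BasePainCat can be the split in SAP 4.2.6 ("Baseline pain VRS scores for dysmenorrhea (DYS), non-menstrual pelvic pain (NMPP), and dyspareunia: < median value at baseline", against at or above it), using the endpoint's own baseline score, or quartiles of that score. If stratified, keep the per-arm call unstratified, and note that the strata only partly align the two odds ratios.

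The required change costs one extra procedure call. The optional one costs a sentence or one derived variable. No new data are needed.

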4.6.2.3. Per Protocol Analysis

The primary analysis as described in Section 4.6.2.1.2 will be repeated using the Per Protocol Set.

4.6.2.4. Subgroup analysis

The primary analysis model and descriptive statistics as described in Section 4.6.2.1.2 will be repeated for each co-primary endpoint by subgroups as specified in Section 4.2.6.

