13.5.4 Additional Efficacy Analysis

Endpoints that are collected daily using the eDiary will be based on the 28 calendar days immediately prior to and including the day of the corresponding visit, or the 28 calendar days immediately prior to and including the last dose date for subjects who discontinue treatment prior to the visit in question (or fewer if treatment is stopped less than 4 weeks after randomization), in order to estimate the treatment effect of while under treatment. Corresponding baseline values will be calculated based on the two complete menstrual cycles during screening, which may not be exactly 28 days each.

The values for other endpoints are defined as the value at the corresponding visit, or the closest completed assessment to the last dose date for subjects who discontinue treatment prior to the visit in question.

An additional analysis of the co-primary endpoints will be conducted that considers all subjects who prematurely discontinue the study treatment before the Month 3 visit as non-responders. These are composite endpoints that estimate the proportion of subjects with clinically meaningful reduction in pain, a stable or decreased use of rescue medication and who complete 3 months of treatment.

An additional analysis of the co-primary endpoints will be also conducted to estimate the effect of treatment policy rather than that of while on treatment. A reference based multiple imputation approach will be used for subjects who discontinue the study prior to Month 3. Further details will be provided in the SAP.

All exploratory efficacy endpoints will be summarized by descriptive statistics for each treatment group, for each time point, including summaries of change from baseline when applicable. Individual linzagolix versus placebo treatment group comparisons will be made.

In general, between group comparisons for continuous endpoints will be analyzed via analysis of (co)-variance. Between-group comparisons for binary endpoints will be analyzed via logistic regression. Between-group comparisons for ordinal categorical data will be analyzed using a Mantel-Haenszel test, or using Koch's method when there is also a baseline covariate. Full details describing the derivation and analyses of each exploratory endpoint will be provided in the SAP.

Sub-group analyses based on demographic and baseline characteristics will be performed for each co-primary endpoint and select secondary endpoints, and will be specified in the SAP.

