4.8.3. Bone Mineral Density (BMD) by DXA

BMD of the femoral neck, total hip and lumbar spine will be assessed by DXA at Baseline, Month 6 and Month 6 follow-up. Unacceptable DXA assessments (accepted="No") will not be summarized (hip, and spine and femur considered separately).

In case of repeated values due to BMD loss \geq 5%, the initial scan will be used in summaries. Initial and repeated scan values will be reported in the listings.

Calibrated values should be provided once all cross-calibration data are made available to the vendor in charge of the scan assessment. These calibrated values will be used in the summary tables if available, otherwise initial values will be considered.

BMD values and corresponding Z-scores will be summarized for each treatment group. The within-group percent changes from baseline for BMD values will also be summarized, including 2-sided 95% confidence intervals.

Percent change from baseline to Month 6 and Month 6 follow-up will be described and will also be summarized in categories of percent change with the following classes:

- No change or increase,
- Decrease ≤ 3%,
- Decrease > 3% and $\leq 5\%$,
- Decrease > 5% and \leq 7%,
- Decrease > 7% and \leq 8%,
- Decrease > 8%.

The percent changes from baseline to Month 6 will be compared between each of the linzagolix groups and the placebo group via analysis of covariance with treatment group as the main effect (three values) and including the baseline as a covariate.

Sample SAS code (SAS code will be fully validated at the analysis stage) for analysis of covariance:

```
Proc GLM data=dataset order=internal;
        Class Treat;
        Model BMD_pchg = BaselineBMD Treat;
        LSMEANS Treat / at means pdiff= control('1') alpha=0.05 cl adjust=bon;
        ODS OUTPUT lsmeans=lsm diff=pvals lsmeancl=lsmeancl
lsmeandiffcl=lsmeandiffcl;
Run;
```

All data will be listed.

A listing of BMD for subjects who discontinued treatment will be provided.

CRS-BS-TP-000005 V 1.0

Page 93 of 127

Cytel Confidential: This is a controlled document and shall not be changed, saved, copied or reproduced by any unauthorized

Sponsor:	ObsEva		
Protocol:	18-OBE2109-003		
Document Version No.:	V5.0	Document Date:	13-JUN-2022

Subgroup analyses by race, age groups 1 and 2, weight and BMI groups 1 and 2 will be performed for BMD, including descriptive summaries, percent changes categories summaries and analysis of covariance.

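### The SAP repeats the co-primary significance tests in 31 subgroup levels and plans no treatment-by-subgroup interaction, so nothing planned tests whether the effect differs between subgroups

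*SAP*

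**What the plan says.** Protocol 13.5.4 announces the analyses and leaves the detail to the SAP: "Sub-group analyses based on demographic and baseline characteristics will be performed for each co-primary endpoint and select secondary endpoints". SAP 4.2.6 lists the factors, for example "Race: Black or African American, Other". SAP 4.6.2.4 then gives the method: "The primary analysis model and descriptive statistics as described in Section 4.6.2.1.2 will be repeated for each co-primary endpoint by subgroups". The section it points to, 4.6.2.1.2, fits a logistic regression with three-level treatment and baseline pain score only. Its output is fixed there: "Estimated odds-ratios and 97.5% intervals of proportions of responders of linzagolix treatment groups versus placebo will be presented, along with Bonferroni corrected p-values".

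For BMD, SAP 4.8.3 plans subgroup analyses by race, both age groupings, weight and both BMI groupings, "including descriptive summaries, percent changes categories summaries and analysis of covariance".

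Neither document mentions a treatment-by-subgroup interaction. Neither gives the subgroup analyses a place in the testing hierarchy or calls them exploratory. Other analyses outside the hierarchy do get such wording: SAP 4.2.5 describes the by-visit response rates as supportive and not fully controlled, and SAP 4.6.4 says the additional secondary endpoints are not fully controlled.

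**The concern.** The question a subgroup analysis should answer is whether the treatment effect differs between levels of a factor. The planned analysis answers another one: whether each level, taken alone, reaches significance against placebo. One level reaching significance while its neighbour does not is no evidence that the effect differs, because the levels differ in size and therefore in power.

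Misreading can go two ways. If linzagolix works equally well in everyone, the tables will still contain non-significant levels, and a reader may conclude that it fails in small groups, such as women aged 45 or over or with BMI below 20. If it does not work, a chance-significant level would be shown with the same statistic and threshold as the co-primary test. The SAP's change log (section 5) records that age and BMI subgroups were added after an FDA request, so these tables are likely to be read closely.

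**Working it through.** **Inputs.** From SAP 4.1: 150 women per arm; two-sided 0.025 per dose (raw p-value doubled, then compared with 0.05); DYS response 14.6% on placebo, 48.6% on 75 mg and 64.7% on 200 mg; NMPP response 18.8% on placebo and 42.1% on active. From SAP 4.2.6: the factors and levels. The documents give no share of women in each level, so shares are assumed.

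**1. The plan's own power.** Two-proportion test, pooled variance, critical value 2.241, n = 150 per arm:
- NMPP: null SE = √(2 × 0.3045 × 0.6955 / 150) = 0.0531; alternative SE = √((0.188 × 0.812 + 0.421 × 0.579) / 150) = 0.0514; (0.233 − 2.241 × 0.0531) / 0.0514 = 2.22, so power is 98.7%.
- DYS: above 99.99% for both doses.
- Both endpoints together: 98.7% for each dose. The stated figure of more than 95% is reproduced.

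**2. Number of tests.** Race 2, ethnicity 2, age group 1 2, age group 2 4, weight 2, BMI group 1 2, BMI group 2 4, baseline analgesic use 2, baseline DYS, NMPP and dyspareunia 2 each (6), time since diagnosis 3, pregnancy history 2. The sum is 31. Then 31 × 2 endpoints × 2 doses = 124.

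**3. Power within one level, NMPP.** Difference 0.421 − 0.188 = 0.233; SE = √((0.188 × 0.812 + 0.421 × 0.579) / n).
- A quarter of each arm, n = 37.5: SE = 0.103, z = 2.27 against 2.241, power about 51%. The pooled-variance formula with n = 37 gives 47%.
- A tenth of each arm, n = 15: SE = 0.163, z = 1.43, power about 21%. The pooled formula gives 19%.

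**4. Simulation of all 124 tests.** Two set-ups were run, both with 150 per arm, one placebo arm shared by both doses, and overlapping factors.
- A: unadjusted Wald test of the log odds ratio, endpoint correlation 0.5, 2,000 trials per scenario, two sets of shares (unequal, e.g. 10/45/35/10% for age group 2; more even, e.g. 25% each).
- B: pooled z-test, endpoint correlation 0, 0.3 and 0.6, 4,000 trials per scenario, one set of shares (e.g. 8% in the smaller race level, 8% in the smaller ethnicity level, 15% with no analgesic use).

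| Truth | Result | A | B |
|---|---|---|---|
| Same effect in all, design rates | Mean non-significant of 124 | 30.3 (unequal), 21.7 (even) | about 27 |
| Same effect in all, design rates | Trials with at least one non-significant | all | all |
| Same effect in all, design rates | Trials with at least one wrong-direction estimate | not recorded | 67% to 69% |
| No effect | Trials with at least one significant, either direction | 0.60 (unequal), 0.65 (even) | 0.77 to 0.80 |
| No effect | Trials with at least one significant favouring linzagolix | not recorded | 0.46 to 0.49 |

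For comparison, 124 independent tests would give 124 × 0.025 = 3.1 expected false positives and 1 − 0.975^124 = 0.957 for at least one. The overlap between factors and the shared placebo arm bring that probability down to the simulated values.

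**5. The alternative.** One interaction contrast per factor, endpoint and dose: 13 × 2 × 2 = 52. At 0.025 each, 52 × 0.025 = 1.3 are expected by chance, and 1 − 0.975^52 = 0.73 is the probability of at least one if they were independent. Testing both doses jointly halves the count to 26.

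**The case against.** The strongest reply is that no subgroup result can trigger a claim. Under SAP 4.2.5 a dose must win on both co-primary endpoints in the full population before the fixed sequence starts, and a dose that fails there is not considered more efficacious than placebo. This stands. A reader might set the 60% to 80% against the trial's 0.05 and infer that type I error is inflated more than tenfold. The documents do not support that: the 0.05 governs the confirmatory family, and no subgroup test belongs to it.

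A reader might also infer that chance positives are as certain as chance negatives. They are not. They are likely rather than near-certain, they arise only if there is no effect, and fewer than half of the no-effect trials in set-up B had one favouring linzagolix. At the design rates, a significant level favouring linzagolix is a true positive.

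Third, printing results "along with Bonferroni corrected p-values" is not in itself a confirmatory signal in this SAP. The same two-dose correction is applied to analyses that it calls supportive or not fully controlled (4.2.5, 4.6.4). The protocol also places subgroups under additional efficacy analysis, although the SAP places them under the primary endpoint. This weakens the worry about labelling but does not supply a test of difference.

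Fourth, for BMD a reader might infer a separate ANCOVA in each level. SAP 4.8.3 does not say so; it leaves the form of the subgroup model open.

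Finally, interaction tests bring multiplicity of their own, as step 5 shows. That is true, but they address the question that the within-level tests leave unasked.

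**Conclusion.** The point holds as a gap in analysis and interpretation. The counts of 31 levels and 124 tests follow directly from the SAP, as does the absence of any interaction term: the model being repeated contains only treatment and baseline pain. At the design rates with a homogeneous effect, chance non-significant levels are near-certain under every set of shares tried. Their average number, 22 to 30 of 124, and the 60% to 80% for at least one chance-significant level under no effect depend on assumed level shares and on simplified tests that leave out the baseline pain adjustment. They should be read as orders of magnitude. Confirmatory type I error, sample size and the efficacy claim are unaffected. No BMD calculation was made, so for BMD the point is only that the model form should be stated.

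**What to change.** Replace the method in SAP 4.6.2.4. For each factor in 4.2.6 and each co-primary endpoint, fit one logistic model to the FAS with treatment, baseline pain score, subgroup and treatment-by-subgroup interaction. Report the subgroup odds ratios with confidence intervals and the interaction p-value, in place of within-level Bonferroni p-values. State that all subgroup analyses are exploratory and outside the error control of 4.2.5. In 4.8.3, specify the BMD subgroup ANCOVA with a treatment-by-subgroup term.

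The cost is SAP wording and one model per factor instead of one per level, with no additional data or participants. The downside should be written into the text: interaction tests have low power and there are 52 dose-specific contrasts, so neither a single significant interaction nor the absence of one is conclusive. How to handle very sparse levels is a separate choice for the trial team.
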